1.1.2 Study Drug

mTOR Inhibitors

The mTOR serine/threonine kinase has a central role in regulating cellular growth and metabolism in response to external environmental factors.^(1,2) The mTOR kinase binds with other proteins to form 2 distinct multiprotein complexes, TORC1 and TORC2. The TORC1 complex is stimulated by growth factors and amino acids and regulates cell growth by controlling the activity of the ribosomal protein S6 kinase (S6K) and eukaryotic initiation factor 4-binding protein (4E-BP1).⁽³⁾ The TORC2 complex is activated by growth factors and promotes cell survival, proliferation, and actin cytoskeleton organization by phosphorylating and activating kinases, such as serine/threonine-specific protein kinase (AKT; also known as protein kinase B), which is a regulator of apoptosis.^(4,5)

Two major classes of mTOR inhibitors are under development: allosteric inhibitors and adenosine triphosphate (ATP)-competitive inhibitors. The first-generation, or allosteric, inhibitors include rapamycin and the related analogs or rapalogs temsirolimus, everolimus, and ridaforolimus. The rapalogs effectively inhibit phosphorylation of S6K but only partially inhibit the phosphorylation of 4E-BP1, which regulates cap-dependent translation of transcripts for cell survival, proliferation, and angiogenesis.⁽²⁾ Thus, rapamycin and the rapalogs are only partial inhibitors of TORC1.⁽²⁾

The ATP-competitive inhibitors (also known as mTOR kinase inhibitors or TORkinibs), such as MLN0128, bind to the catalytic domain of mTOR and thus inhibit both TORC1 and

MLN0128**Clinical Study Protocol C31002 Protocol Amendment 2**

TORC2 complexes, including the rapamycin-insensitive or -resistant actions of TORC1, such as phosphorylation of 4E-BP1.^(6, 7, 8)

The rapalogs temsirolimus and everolimus have been approved by the United States (US) Food and Drug Administration (FDA) as monotherapy for patients with advanced renal cell carcinoma (temsirolimus and everolimus), advanced pancreatic neuroendocrine tumors (everolimus), and subependymal giant cell astrocytoma associated with tuberous sclerosis (everolimus). However, resistance to single-agent rapalog therapy occurs and may be related to either incomplete inhibition of the targeted pathway (such as phosphorylation of 4E-BP1 as discussed above) or loss of S6K-mediated feedback inhibition of growth factor receptor signaling leading to paradoxical hyperactive signaling. The normal feedback loop involves activated S6K, which phosphorylates and inactivates insulin receptor substrate-1 and inhibits signaling through the phosphoinositide 3-kinase (PI3K) pathway.^(5, 9) In the presence of rapalogs, the feedback loop is abrogated, leading to continued PI3K signaling, TORC2 activation, and subsequent phosphorylation of AKT at Threonine 308 (T308) and Serine 473 (S473), which markedly enhances the activity of AKT.^(2, 5, 9)

The loss of feedback inhibition by rapalogs has been demonstrated in clinical trials. In an analysis of either paired fresh tumor samples or skin biopsies obtained from 55 patients who received different doses of everolimus either daily or weekly in a phase 1 trial, everolimus inhibited TORC1 in a dose- and schedule-dependent manner with near complete inhibition of S6K.⁽¹⁰⁾ Half the paired tumor samples had a posttreatment increase in the phosphorylation of AKT at S473.⁽¹⁰⁾ These results provide direct evidence that loss of S6K feedback and subsequent PI3K/TORC2-induced activation of AKT occurs commonly in patients with solid tumors receiving single-agent everolimus.

MLN0128 is a potent, highly selective, ATP-competitive inhibitor of mTOR. MLN0128 is mechanistically distinct from the allosteric inhibitors of mTOR (rapamycin and its derivatives, referred to as rapalogs). The rapalogs only partially inhibit TORC1, whereas MLN0128 inhibits both TORC1 (more completely S6K and 4E-BP1) and TORC2. Dual TORC1/2 inhibition mitigates feedback activation of PI3K and AKT, known to cause resistance to TORC1-only inhibitors.⁽¹¹⁾

1.2 Nonclinical Experience

MLN0128 inhibited the human ether-à-go-go related gene (hERG) potassium ion channel with a concentration producing 50% inhibition (IC_{50}) of approximately 175 μ M. Given an in vitro mTOR kinase IC_{50} of 1.1 nM, MLN0128 is not expected to have an effect on the

MLN0128**Clinical Study Protocol C31002 Protocol Amendment 2**

hERG channel at efficacious exposures in humans. Additionally, a Good Laboratory Practice (GLP)-compliant cardiovascular safety study in telemeterized monkeys demonstrated no effects on the body temperature, blood pressure, heart rate, or electrocardiogram (ECG) endpoints. There were also no effects on cardiovascular or respiratory parameters with MLN0128 in GLP-compliant toxicology studies. In the GLP-compliant, single-agent study of MLN0128 in Sprague-Dawley rats, gait effects were observed on Day 28; however, no similar effects have been observed in humans.

The toxicity profile of MLN0128 in rats and monkeys, as established in GLP-compliant repeat-dose studies, is consistent with pharmacologic inhibition of mTORC1/2 activity. The dose limiting toxicities (DLTs) of MLN0128 in rats and monkeys were secondary to an exaggerated pharmacologic response and consisted of body weight loss and associated clinical observations that included gastrointestinal (GI) distress and decreased activity, appetite, and body temperature. Additional findings in rat and monkey repeat-dose toxicology studies with MLN0128 included bone marrow and lymphoid depletion, GI and skin effects, and effects on glucose and insulin levels, all of which can be monitored in clinical trials. The toxicities seen in the repeat-dose toxicology studies, such as GI effects and glucose and insulin increases, are consistent with the treatment-emergent adverse events (TEAEs), including mucositis and hyperglycemia, which have been observed to date in patients receiving MLN0128.

MLN0128 was negative in the Ames assay, in vivo comet assay, and in vivo micronucleus assay. An in vitro chromosomal aberration assay was positive. Thus, current evidence supports a low risk for genotoxicity for MLN0128.

Recently completed in vitro metabolism experiments in human hepatocytes using ¹⁴C-labeled MLN0128 suggest that MLN0128 is metabolized primarily via CYP1A2 (approximately 31% to 40%), with a minor contribution from CYP3A4 (approximately 11% to 22%). These data suggest that MLN0128 is also metabolized by direct glucuronidation (approximately 22%) and an unidentified non-uridine diphosphate glucuronosyltransferase pathway (approximately 18%). The new data differ from the previous in vitro CYP phenotyping data obtained using recombinant CYP enzymes, which suggested the involvement of CYP2C9 (approximately 35%), CYP2C19 (approximately 28%), and CYP3A4 (approximately 28%) in MLN0128 metabolism.

In addition, physiologically based PK modeling and simulation using the new metabolism data for MLN0128 suggest that the risk for a metabolism-based drug-drug interaction with

MLN0128**Clinical Study Protocol C31002 Protocol Amendment 2**

MLN0128 appears to be low. Therefore, strong CYP1A2 inhibitors and CYP inducers (see Section 14.4) should only be administered with caution and at the discretion of the investigator during the study. Alternative treatments, if available, should be considered.

MLN0128 exhibits an inverse pH dependent aqueous solubility, having low solubility at high pH. pH modifying agents such as proton pump inhibitors (PPIs), H₂-receptor antagonists, or neutralizing antacids that can increase stomach pH can reduce MLN0128 absorption. In this study PPIs are not permitted; however, restricted use of H₂-receptor antagonists and neutralizing antacids is permitted (refer to Section 6.5 and Section 6.6).

Detailed information regarding the nonclinical pharmacology and toxicology of MLN0128 may be found in the [Investigator's Brochure \(IB\)](#).

1.3 Clinical Experience

Single-agent MLN0128 is in clinical development with 2 phase 1 studies: a study in patients with advanced solid malignancies (INK128-001) and a study in patients with relapsed or refractory multiple myeloma or Waldenstrom macroglobulinemia (INK128-002). A third phase 1 study of MLN0128 is in combination with paclitaxel with or without trastuzumab in patients with advanced solid tumors (INK128-003). These studies have been designed to investigate the safety, pharmacokinetics (PK), pharmacodynamics, and preliminary efficacy of MLN0128 for the treatment of advanced solid tumors and hematologic malignancies either as a single agent or in combination with chemotherapy and/or human epidermal growth factor receptor 2 (HER2)-targeting agents. A phase 1b/2 study of MLN0128 in combination with exemestane or fulvestrant therapy in women with estrogen receptor positive (ER+)/HER2 negative (HER2-) advanced or metastatic breast cancer (Study C31001) is enrolling patients. Additionally, the combination of MLN0128 with MLN1117 (an oral PI3K α inhibitor) is being evaluated in a phase 1b study in adult patients with advanced nonhematologic malignancies (Study C32001).

Further details on these studies are provided in the [IB](#).

1.4 Study Rationale

MLN0128 is currently in phase 1 clinical investigation. In May 2012, the US FDA recommended that the effect of MLN0128 on rate-corrected QT interval (millisec) of electrocardiograph (QTc) be investigated before initiating phase 3 studies.

MLN0128**Clinical Study Protocol C31002 Protocol Amendment 2**

Assessment of the potential of an investigational agent to cause QTc prolongation as a biomarker for ventricular tachycardia is an essential component of new drug development, as drugs that prolong the QTc interval pose an increased risk for ventricular tachycardia and sudden cardiac death. While ECG data are collected during early clinical studies, often these data are not sufficient to provide a high degree of confidence in evaluation of the potential of a study drug to prolong the QT interval. Dedicated QTc studies are advantageous because extensive ECG data is collected prior to and immediately following dosing of the investigational agent. ECG measurements can be made to coincide with clinically relevant maximal concentrations of the investigational agent to provide a more robust assessment of the effect of the investigation agent on QTc interval.

The primary objective of this dedicated QT study is to characterize the effect of a single dose of 40 mg MLN0128 on the QTc interval in patients with advanced solid tumors. Two doses and schedules of MLN0128 are currently being investigated: 5 mg every day (QD) and 40 mg QW. The 40 mg QW is currently the highest dose of MLN0128 under clinical investigation. The 40 mg dose of MLN0128 is also the single agent maximum tolerated dose (MTD) of MLN0128 in the QW dosing schedule. MLN0128 does not accumulate in plasma to any meaningful extent with QD dosing and the maximum plasma concentration of MLN0128 with 5 mg QD dosing is unlikely to exceed those expected at the 40 mg QW dose of MLN0128. The 40 mg dose of MLN0128 will allow for the assessment of the effect of MLN0128 on QTc interval at its highest anticipated plasma concentration.

Since this study will be conducted in patients with advanced solid tumors, the study does not include placebo or a positive control (ie, moxifloxacin). In addition, since the 40 mg dose of MLN0128 represents its single agent MTD in the QW dosing schedule and is the highest dose of MLN0128 administered in clinical studies, the design of this dedicated QT study does not include a supratherapeutic dose of MLN0128. The collection of serial time-matched baseline ECGs should account for circadian changes, within patient inter-occasion variability in ECGs, and the determination of individual baseline corrected QTc (QTcI). ECGs will be collected in triplicate to further minimize variability.

Time-matched collection of serial PK data of MLN0128 for concentration-QTc analysis will enable the understanding of changes in QTc with plasma concentration and projection of the effect of MLN0128 on QTc at doses that were not evaluated in this study.

MLN0128 is known to induce nausea and vomiting at the 40 mg dose. To mitigate this effect, patients will receive an antiemetic agent (0.25 mg palonosetron) before receiving the single dose of MLN0128. No significant effect of palonosetron on QT interval has been

MLN0128**Clinical Study Protocol C31002 Protocol Amendment 2**

observed at doses up to 2.25 mg in a thorough QT assessment,⁽¹²⁾ thus, no effect on QT interval is anticipated with the prophylactic use of palonosetron during this study.

1.5 Potential Risks and Benefits

The most common TEAEs observed with MLN0128 are consistent with the pharmacodynamic mechanism of mTOR inhibition that is also seen with rapalogs (TORC1 inhibition) or other dual mTORC1/2 inhibitors. The TEAEs observed across the MLN0128 single-agent studies include diarrhea, fatigue, vomiting, rash, mucosal inflammation, asthenia, dysgeusia, thrombocytopenia, stomatitis, and blood creatinine increased. In general, toxicities observed to date have been mostly Grade 1 or Grade 2 and are manageable with supportive care and/or dose interruption or dose reduction of MLN0128.

Risk mitigation strategies for potential adverse events (AEs) include, but are not limited to, strict application of the study inclusion and exclusion criteria, frequent monitoring of clinical and laboratory results, guidelines for management and prophylaxis of potential toxicities, criteria for dose modification, and regular monitoring of AEs and serious adverse events (SAEs) by the sponsor. Refer to Section 6.8 for additional information.

The benefits of MLN0128 are discussed in Section 1.1.

Further details are presented in the MLN0128 [IB](#).

2. STUDY OBJECTIVES**2.1 Primary Objective**

The primary objective is:

- To characterize the effect of a single dose of 40 mg MLN0128 on the electrocardiographic QT/QTc interval in patients with advanced solid tumors

2.2 Secondary Objectives

The secondary objectives are:

- To evaluate the safety, tolerability, and pharmacokinetics of MLN0128 in patients with advanced solid tumors

3. STUDY ENDPOINTS

3.1 Primary Endpoint

The primary endpoint is:

- Change in QTcI from time-matched baseline (Screening; Day -1) to Cycle 1, Day 1

3.2 Secondary Endpoints

The secondary endpoints are:

- AEs, SAEs, assessments of clinical laboratory values, and vital sign measurements
- Change from time-matched baseline (Screening; Day -1) in QTc with Bazett correction (QTcB), QTc with Fridericia correction (QTcF), QRS, PR, and heart rate on Cycle 1, Day 1
- PK parameters, including, but not limited to, single-dose maximum (peak) concentration (C_{max}), single-dose first time of occurrence of maximum (peak) concentration (T_{max}), area under the plasma concentration versus time curve from zero to the last measurable concentration (AUC_t), area under the plasma concentration versus time curve from zero to infinity (AUC_{inf}), and terminal disposition half-life ($t_{1/2}$)

4. STUDY DESIGN

4.1 Overview of Study Design

This is an open label, single-arm, multicenter study to evaluate the effect of a single dose of 40 mg MLN0128 on the electrocardiographic QT/QTc interval in patients with advanced solid tumors.

The study will enable collection of time-matched PK and ECG data before and after MLN0128 administration at the time points specified in the [Schedule of Events](#). A central ECG reader will be used and continuous 12-lead digital ECGs will be obtained using a Holter H12+ ECG recorder. All planned 12-lead ECG collections will be obtained in triplicate.

MLN0128**Clinical Study Protocol C31002 Protocol Amendment 2**

On the morning of Screening; Day -1 baseline measurements of serial triplicate ECGs (0-10 hours) will be obtained. Three Holter ECGs will be extracted at the time points matching the Cycle 1, Day 1 PK/ECG sampling times. As the Screening; Day -1 baseline evaluations serve as the time-matched baseline for the corresponding Cycle 1, Day 1 PK/ECG assessments, the 0-hour time point on Screening; Day -1 should coincide with the clock time of MLN0128 dosing on Cycle 1, Day 1 (the 0-hour time point on Cycle 1, Day 1). The clock time of all other ECG assessments on Screening; Day -1 should also coincide with the clock time of PK/ECG assessments for Cycle 1, Day 1. After collection of the planned 10-hour ECG sample on Cycle 1, Day 1, the Holter recorders will not be removed and patients will be furloughed from the study site.

On Screening; Day -1 and Cycle 1, Day 1, patients will be given the option to report to the site fasted or after having a light morning meal as long as the meal has been completed at least 2 hours before the scheduled baseline triplicate ECG on each day. If patients report to the site fasted, they should do so with adequate time (approximately 3 hours before the scheduled baseline triplicate ECG) in order to eat standard, light breakfast provided by the site that must be completed at least 2 hours before the scheduled baseline triplicate ECG on each day. Patients will be instructed not to eat for the next 6 hours (ie, 2 hours before the 0-hour, predose time point and until completion of the collection of the 4-hour postdose PK/ECG assessments). A standard, light lunch will be provided. Light meals will be administered at the same times on Screening; Day -1 and Cycle 1, Day 1.

For the Screening; Day -1 and Cycle 1, Day 1 study visits, fasting serum glucose will be measured at the clinical facility. In addition, all patients will be issued a glucometer and trained to use it to monitor their daily predose fasting blood glucose (FBG) levels at home for the days on which glucose is not measured at the clinic. Patients will be instructed to notify the study staff immediately with any abnormal readings (ie, ≥ 150 mg/dL) for further instructions on the management of hyperglycemia. In-home glucose monitoring is not required on days when fasting glucose is measured in the clinic.

To mitigate nausea and vomiting known to occur at a 40 mg dose of MLN0128, patients will be administered an antiemetic agent (0.25 mg palonosetron) on Cycle 1, Day 1.

After collection of the 10-hour postdose PK/ECG assessment on Cycle 1, Day 1, patients will be furloughed from the study site. The Holter recorders will not be removed during this furlough period.

MLN0128**Clinical Study Protocol C31002 Protocol Amendment 2**

On Cycle 1, Day 2 and Cycle 1, Day 3, patients may eat and drink up to approximately 2 hours before arriving at the study site for PK/ECG evaluations.

On Cycle 1, Day 2, patients will report to the clinical facility at least 1 hour before the 24-hour postdose PK/ECG (triplicate) assessments. After the PK/ECG assessments are completed, the Holter recorders will be removed and patients will be furloughed from the study site.

On Cycle 1, Day 3, patients will report to the clinical facility at least 1 hour before the 48-hour postdose assessments, which will represent the final study endpoint-specific planned PK/ECG assessments.

Patients may continue to receive MLN0128 if, in the opinion of the investigator, the patients are deriving clinical benefit, until they experience disease progression. Patients continuing treatment with MLN0128 at the discretion of the investigator will receive a dose of MLN0128 up to 30 mg QW. Dose escalation will not be permitted, and a maximum of 2 dose reductions (for patients experiencing study drug-related toxicity) will be permitted. Patients will return to the study site for follow-up visits at the time points in the [Schedule of Events](#). Treatment may continue until disease progression, unacceptable MLN0128-related toxicity, withdrawal of consent, or for up to 12 months (whichever occurs first).

All patients enrolled in the study will attend the End-of-Study (EOS)/Early Termination visit 30 (to 40) days after receiving their last dose of study drug.

Toxicity will be evaluated according to National Cancer Institute Common Terminology Criteria for Adverse Events (NCI CTCAE), Version 4.03, effective date 14 June 2010.⁽¹³⁾ DLTs are defined in Section [6.3](#).

AEs will be assessed, and laboratory values, vital signs, and ECGs will be obtained to evaluate the safety and tolerability of MLN0128.

Radiological evaluations (computed tomography [CT] scan or magnetic resonance imaging [MRI] as clinically indicated) will be obtained at baseline and Cycle 3, Day 28, after which point CT (with contrast) or MRI may be performed every 3 cycles at the investigator's discretion as clinically indicated, according to standard of care.

MLN0128
Clinical Study Protocol C31002 Protocol Amendment 2

4.2 Number of Patients

Approximately 30 patients will be enrolled in this study. Patients will be enrolled from approximately 6 study centers in the US. Enrollment is defined as the time of the initiation of the first dose of study drug.

Patients who are withdrawn from treatment before completing study-required PK/ECG assessments for reasons other than DLTs will be replaced.

4.3 Duration of Study

Patients may receive MLN0128 until they experience disease progression. Patients will discontinue treatment if they have an unacceptable MLN0128-related toxicity. The maximum duration of treatment will be 12 months unless, after discussion between the investigator and sponsor, it is determined that a patient would derive benefit from continued therapy beyond 12 months.

Patients will attend an EOS/Early Termination visit 30 (to 40) days after receiving their last dose of study drug to permit the detection of any delayed treatment-related AEs.

It is anticipated that this study will last for approximately 12 months.

5. STUDY POPULATION

5.1 Inclusion Criteria

Each patient must meet all of the following inclusion criteria to be enrolled in the study:

1. Men or women patients 18 years or older.
2. Patients must have a radiographically or clinically evaluable solid tumor for which standard-of-care therapy has failed; however, measurable disease as defined by modified Response Evaluation Criteria in Solid Tumors criteria (Version 1.1)⁽¹⁴⁾ is not required for participation in this study.
3. Patients with a history of brain metastasis may be eligible for the study provided all of the following criteria are met:
 - Brain metastases which has been treated

MLN0128**Clinical Study Protocol C31002 Protocol Amendment 2**

- No evidence of disease progression or hemorrhage after treatment
- Off-treatment with dexamethasone for 28 days before administration of the first dose of MLN0128
- No ongoing requirement for dexamethasone or anti-epileptic drugs

4. Eastern Cooperative Oncology Group (ECOG) performance status of 0 or 1 (refer to Section 14.1).

5. Female patients who:

- Are postmenopausal for at least 1 year before the screening visit, OR
- Are surgically sterile, OR
- If they are of childbearing potential, agree to practice 2 effective methods of contraception, at the same time, from the time of signing the informed consent through 3 months after the last dose of study drug, or
- Agree to practice true abstinence, when this is in line with the preferred and usual lifestyle of the subject. (Periodic abstinence [eg, calendar, ovulation, symptothermal, postovulation methods] and withdrawal are not acceptable methods of contraception.)

Male patients, even if surgically sterilized (ie, status postvasectomy), who:

- Agree to practice effective barrier contraception during the entire study treatment period and through 3 months after the last dose of study drug, or
- Agree to practice true abstinence, when this is in line with the preferred and usual lifestyle of the subject. (Periodic abstinence [eg, calendar, ovulation, symptothermal, postovulation methods for the female partner] and withdrawal are not acceptable methods of contraception.)

6. Voluntary written consent must be given before performance of any study-related procedure not part of standard medical care, with the understanding that consent may be withdrawn by the patient at any time without prejudice to future medical care.

7. Clinical laboratory values as specified below within 28 days before the first dose of study drug:
 - Total bilirubin must be $\leq 1.5 \times$ the upper limit of normal (ULN)
 - Alanine aminotransferase (ALT) and aspartate aminotransferase (AST) $\leq 2.5 \times$ the ULN. ALT and AST may be $\geq 5 \times$ the ULN if the elevation can be reasonably ascribed to the presence of metastatic disease in liver.
 - Creatinine clearance ≥ 50 mL/min based either on Cockcroft Gault estimate or based on a 12- or 24-hour urine collection. (refer to Section 14.3)
 - Absolute neutrophil count $\geq 1.5 \times 10^9$ /L; platelet count $\geq 100 \times 10^9$ /L; hemoglobin ≥ 10 g/dL
 - Fasting glucose ≤ 120 mg/dL and fasting triglycerides ≤ 300 mg/dL
8. Left ventricular ejection fraction (LVEF) within 5 absolute percentage points of institutional standard of normal, as measured by echocardiogram or multiple gated acquisition (MUGA) scan, within 28 days before the first dose of study drug (ie, if the institutional normal is 50%, LVEF may be as low as 45% to be eligible).
9. Ability to swallow oral medications, willingness to perform mucositis prophylaxis, and suitable venous access for the study-required blood sampling.
10. Patients requiring chronic treatment with H₂-receptor antagonists or neutralizing antacids are eligible; however, the most recent dose must have been more than 48 hours with H₂-receptor antagonists and more than 4 hours with neutralizing antacids before receiving the first dose of MLN0128. Treatment with H₂-receptor antagonists or neutralizing antacids is permitted after completing the required PK/ECG assessments on Cycle 1, Day 3 within the specified windows (refer to Section 6.6).

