Radiological evaluations (computed tomography [CT] scan or magnetic resonance imaging [MRI] as clinically indicated) will be obtained at baseline and Cycle 3, Day 28, after which point CT (with contrast) or MRI may be performed every 3 cycles at the investigator's discretion as clinically indicated, according to standard of care.

Study Population: Men or women 18 years or older with a radiographically or clinically evaluable solid tumor for which standard-of-care therapy has failed may be enrolled in this study; however, measurable disease as defined by modified Response Evaluation Criteria in Solid Tumors criteria is not required. Patients with a history of brain metastasis may be eligible provided all of the following criteria are met: treated brain metastases; no evidence of disease progression or hemorrhage after treatment; off-treatment with dexamethasone for 28 days before administration of the first dose of MLN0128; and no ongoing requirement for dexamethasone or anti-epileptic drugs. Eligible patients must have an Eastern Cooperative Oncology Group performance status of 0 or 1 and the following clinical laboratory values within 28 days before the first dose of MLN0128: total bilirubin $\leq 1.5 \times$ the upper limit of normal (ULN); alanine aminotransferase and aspartate aminotransferase $\leq 2.5 \times$ the ULN; creatinine clearance ≥ 50 mL/min; absolute neutrophil count $\geq 1.5 \times 10^9/L$; platelet count $\geq 100 \times 10^9/L$; hemoglobin ≥ 10 g/dL; fasting glucose ≤ 120 mg/dL and fasting triglycerides ≤ 300 mg/dL. Left ventricular ejection fraction must be within 5 absolute percentage points of institutional standard of normal within 28 days before the first dose of MLN0128.

[figure not shown]
Patients with a history of leptomeningeal disease or spinal cord compression or tumors with involvement of the mediastinum are not eligible. Patients with a diagnosis of diabetes mellitus may not be enrolled in the study. Patients with a history of any of the following within 6 months before study entry are also not eligible: ischemic myocardial event; ischemic cerebrovascular event; requirement for inotropic support (excluding digoxin) or serious (uncontrolled) cardiac arrhythmia

MLN0128**Clinical Study Protocol C31002 Protocol Amendment 2**

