5.2 Exclusion Criteria

Patients meeting any of the following exclusion criteria are not to be enrolled in the study.

1. Female patients who are lactating and breastfeeding or have a positive serum pregnancy test during the screening period.

2. Any serious medical or psychiatric illness that could, in the investigator's opinion, potentially interfere with the completion of treatment according to this protocol.
3. Treatment with any investigational products within 14 days before the first dose of study drug and systemic anticancer therapy within 28 days before the first dose of study drug
4. Untreated brain metastasis or history of leptomeningeal disease or spinal cord compression.
5. Tumors with involvement of the mediastinum.
6. Failure to recover from the reversible effects of prior anticancer therapies with the exception of alopecia, and after-effects associated with prior tyrosine kinase inhibitor therapy such as hair depigmentation, hypothyroidism, and/or splinter hemorrhage.
7. Systemic corticosteroid (inhalers are allowed) within 7 days before the first dose of study drug.
8. Manifestations of malabsorption due to prior GI surgery, GI disease, or for an unknown or other reason that may alter the absorption of MLN0128.
9. Diagnosis of diabetes mellitus; patients with a history of transient glucose intolerance due to corticosteroid administration may be enrolled if all other inclusion/exclusion criteria are met.
10. History of any of the following within 6 months before study entry:
 - Ischemic myocardial event, including angina requiring therapy and artery revascularization procedures
 - Ischemic cerebrovascular event, including transient ischemic attack and artery revascularization procedures
 - Requirement for inotropic support (excluding digoxin) or serious (uncontrolled) cardiac arrhythmia (including atrial flutter/fibrillation, ventricular fibrillation, or ventricular tachycardia)
 - Placement of a pacemaker for control of rhythm

- New York Heart Association Class III or IV heart failure
- Pulmonary embolism

11. Significant active cardiovascular or pulmonary disease at study entry, including:

- Uncontrolled high blood pressure (ie, systolic blood pressure > 180 mmHg, diastolic blood pressure > 95 mmHg)
- Resting pulse rate of < 50 beats per minute or > 100 beats per minute at screening or predose
- Pulmonary hypertension
- Uncontrolled asthma or O₂ saturation $< 90\%$ by arterial blood gas analysis or pulse oximetry on room air

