- Significant valvular disease; severe regurgitation or stenosis by imaging independent of symptom control with medical intervention, or history of valve replacement
- Medically significant (symptomatic) bradycardia
- History of arrhythmia requiring an implantable cardiac defibrillator

12. Requirement for QT-prolonging drugs with a risk of causing torsades de pointes (TdP). Patients on a stable dose of drugs with a conditional or possible risk of QT prolongation may be considered.

13. Baseline prolongation of QTc (eg, repeated demonstration of QTcF > 430 ms for men and QTcF > 450 ms for women, or TdP); other abnormal ECG findings deemed clinically significant by the investigator or which would interfere with determination of the QT interval, such as bundle branch block, abnormal T waves or pathological U waves.

14. History of thoracic surgery, Brugada syndrome, history of congenital long QT syndrome (LQTS; or family history of LQTS), or major surgery within 14 days before the first dose of study drug

15. Clinically significant comorbidities such as uncontrolled pulmonary disease, active central nervous system disease, active infection, serious infection within 14 days before the first dose of study drug, or any other condition that could compromise study participation by the patient.
16. Patients requiring daily or chronic use of PPI and/or having taken a PPI within 7 days before receiving the first dose of study drug.

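### The liver-metastasis exception in inclusion criterion 7 is written as a floor (≥ 5 × ULN), so it leaves ALT and AST without an upper limit

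*Protocol*

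**What the plan says.** Criterion 7 in Protocol Section 5.1 lists laboratory limits to be met within 28 days before the first dose. For transaminases the general rule is "Alanine aminotransferase (ALT) and aspartate aminotransferase (AST) $\leq 2.5 \times$ the ULN". The sentence that follows gives the exception: "ALT and AST may be $\geq 5 \times$ the ULN if the elevation can be reasonably ascribed to the presence of metastatic disease" in the liver. The same criterion holds total bilirubin to no more than 1.5 × ULN.

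The Protocol Summary (Study Population) repeats the general limit, "alanine aminotransferase and aspartate aminotransferase $\leq 2.5 \times$ the ULN", and does not mention an exception.

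Section 5.1 requires every inclusion criterion to be met. Section 1.5 names "strict application of the study inclusion and exclusion criteria" among the risk mitigation strategies. The SAP does not deal with eligibility.

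**The concern.** The two transaminase sentences point in opposite directions. The first says how high a value may be. The second is meant to allow a higher value when liver metastases explain it, but it states a minimum. A site applying the criterion as written would turn away a patient with liver metastases at 4 × ULN and accept one at 20 × ULN. Nothing in the documents explains why the milder elevation should be refused and the worse one accepted.

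This is an operative rule. Section 6.1 requires all criteria for administration to be met and documented before dosing, and the dose is 40 mg, which Section 1.4 describes as the single-agent MTD on the weekly schedule. Section 1.2 reports hepatocyte data pointing to CYP1A2, CYP3A4 and glucuronidation as routes of metabolism, so liver status could affect exposure, although the documents give no size for that effect.

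About six centers will enroll. They could reasonably settle on different rules: the synopsis limit, the literal floor, no limit at all, or an assumed ceiling of 5 × ULN.

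**Working it through.** There is no figure to recompute. The check has three parts: the direction of each sign, the set of values each reading admits, and a search for a cap elsewhere.

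**1. Signs in criterion 7 against the synopsis**

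| Item | Section 5.1 | Synopsis |
|---|---|---|
| Total bilirubin (× ULN) | ≤ 1.5 | ≤ 1.5 |
| ALT/AST, general (× ULN) | ≤ 2.5 | ≤ 2.5 |
| ALT/AST, liver metastases (× ULN) | ≥ 5 | not stated |
| Creatinine clearance (mL/min) | ≥ 50 | ≥ 50 |
| Neutrophils (10⁹/L) | ≥ 1.5 | ≥ 1.5 |
| Platelets (10⁹/L) | ≥ 100 | ≥ 100 |
| Hemoglobin (g/dL) | ≥ 10 | ≥ 10 |
| Fasting glucose (mg/dL) | ≤ 120 | ≤ 120 |
| Fasting triglycerides (mg/dL) | ≤ 300 | ≤ 300 |

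Eight of the nine entries appear in both places and agree in direction and value. The ninth, the exception, has no second occurrence to check against. It is also the only sign that runs against the limit it modifies.

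**2. What each reading admits for a patient with liver metastases** (illustrative values)

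| ALT/AST (× ULN) | Literal: ≤ 2.5 or ≥ 5 | Lenient: any value | Corrected: ≤ 5 | Synopsis: ≤ 2.5 |
|---|---|---|---|---|
| 2 | eligible | eligible | eligible | eligible |
| 4 | not eligible | eligible | eligible | not eligible |
| 5 | eligible | eligible | eligible | not eligible |
| 20 | eligible | eligible | not eligible | not eligible |

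The literal reading leaves a gap of 5 − 2.5 = 2.5 × ULN and no maximum. The lenient reading treats the exception as permission and so removes the gap, but it also has no maximum. With the sign reversed, the exception becomes a ceiling 5 / 2.5 = 2 times the general one, with no gap.

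**3. Is the exception capped anywhere else?**

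- The bilirubin limit in criterion 7 still applies to these patients, but it concerns a different analyte.
- Exclusion criterion 2 ("Any serious medical or psychiatric illness that could" interfere with completing treatment, in the investigator's opinion) and the catch-all in criterion 15 ("any other condition that could compromise study participation by the patient") are matters of judgement and give no ALT/AST figure.
- Section 7.4.15 requires the investigator to review chemistry results before enrollment and first dose. Schedule of Events footnote k allows the Day 1 sample up to 4 days before dosing to confirm eligibility. Both compare results with this same criterion.
- The Amendment 2 summary of changes (Section 14.6) lists no change to criterion 7, so the sentence is current text.
- The SAP contains no eligibility limits.

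None of these supplies a maximum for the exception.

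**The case against.** The strongest doubt is that the case turns on one symbol in text read from a PDF by a program. The eight matching signs do not test the disputed one. Elsewhere a sign does appear to be missing: the last recovery row of Table 6-3 has no sign before 2 weeks, while the parallel row of Table 6-6 has one. That stands as a reason to check the source before changing anything. It is weak evidence of a misread here, because a dropped sign is not a reversed one and ≤ is rendered correctly in the same bullet.

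A second argument is that the synopsis, read literally, caps everyone at 2.5 × ULN. It does state a stricter limit, but it omits the exception altogether. Section 5.1 is the operative list, so the synopsis does not supply a ceiling for the exception.

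Third, sites would probably assume that ≤ 5 was meant, and dosing a patient at 20 × ULN would also have to get past the bilirubin limit, the ECOG 0 or 1 requirement, the laboratory review and the two judgement-based exclusions. This lowers the practical risk but leaves the wording wrong. Nor can sites confirm the intended sign, because no passage states it.

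Finally, Sections 1.2 and 1.5 do not name liver toxicity among the effects observed, so the documents support no specific hepatic risk at 40 mg. That is fair, and it limits the weight of the point.

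**Conclusion.** The concern holds. It is a drafting error in an operative eligibility threshold: on either reading, patients whose elevation is ascribed to liver metastases have no upper ALT/AST limit. It should be fixed, but it does not threaten the trial's main result. The consequence is confined to who may be enrolled and dosed.

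The conclusion assumes that the extracted sign matches the source document; if the source shows ≤, the point falls away. That 5 × ULN was intended as a ceiling is an inference from the structure of the two sentences.

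**What to change.** First, check the sign in the source document. If it is ≥, change the exception in Section 5.1, criterion 7, so that ALT and AST up to and including 5 × ULN (≤ 5 × ULN) are allowed when the rise can reasonably be attributed to hepatic metastases. This keeps the protocol's own number, which the sponsor should confirm. Then add the same exception to the Study Population paragraph of the synopsis. Its absence there is an abbreviation and not a separate error, but adding it gives sites one rule in both places.

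The cost is one sign and one clause.
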